## **Analysis of safety endpoints**

### **(1) Adverse events**

List all adverse events that occurred by group. Record the frequency of adverse events related or unrelated with the investigational device by group. For the number of adverse events and the percentage of subjects who had at least 1 adverse event, present the 95% confidence interval in each treatment group. Analyze adverse events separately for local adverse events at the target pressure ulcer and other adverse events.

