	
condition of the pressure ulcer, such as excessive exudates at the study ulcer. Nevertheless, the frequency of additional dressing is limited to twice per day. In case of further exceeding the limited additional dressing (twice per day), the change frequency should be recorded in the Case Report Form.
 
On weekly site visit days, the investigator(or clinical research coordinator) will change the dressing; on other occasions, the subject or guardian will perform self-dressing. The investigator(or clinical research coordinator) trains the subject or guardian on the dressing method at every visit.
 
<Early completion> Subjects who achieve complete healing of the target pressure ulcer within 12 weeks will have early completion. At the early completion visit, all tests scheduled for the Week 12 (End-of-Study) visit should be conducted.
 
<Efficacy assessment> Efficacy assessment is conducted for a total of 12 times at a 1-week interval, after the investigational device application (8d, 15d, 22d, 29d, 36d, 43d, 50d, 57d, 64d, 71d, 78d, 85d). At each efficacy assessment, the investigator(or clinical research coordinator) should take a digital photograph of the target pressure ulcer and retain it as a source document.

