8.2 Exclusion criteria

- 1) Any study ulcer of the NPUAP Stage I, II or IV
- 2) Diabetic ulcer or Venous ulcer (or stasis ulcer)
- 3) Past history of surgical treatment within 1 year or irradiation at the target pressure ulcer within 1 year
- 4) Hypersensitivity reaction to this product or povidone-iodine
- 5) Hyperthyroidism or thyroid disorder requiring drug treatment
- 6) Signs of a current underlying systemic infection (sepsis/bacterial infection/tuberculosis) or cellulitis or osteomyelitis
- 7) Type 1 diabetes
- 8) Current malnutrition
- 9) Heavy smoker: Current smoking level of ≥ 1 pack (20 cigarettes)/day of tobacco
- 10) Drug or alcohol addiction
- 11) Requirement of immunosuppressants during the study or current chemotherapy or radiotherapy
- 12) Application of other investigational product/medical device within 1 month prior to the

investigational device application (1d)

13) Pregnant or breastfeeding women

14) Other renal, hepatic, neurological, immunological disorder that may interfere with the wound healing process, at the discretion of the investigator

9. Target number of subjects and the rationale

The target number of subject enrollment is 20 subjects, with 10 subjects per group.

This study has a purely explorative goal so that no formal sample size calculation will be conducted but it was planned to enroll 10 subjects per group as the minimum sample size to achieve study objectives from a scientific perspective.

- ✓ Medifoam group: 10 subjects
- ✓ Betafoam group: 10 subjects

Even if a subject is withdrawn from the study, the subject will not be replaced.

10. Study method

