14.1 Discontinuation and withdrawal criteria

In case of meeting the following criteria for study device discontinuation, application of the study device and the study should be discontinued, and the reason for discontinuation and findings should be recorded in the Case Report Form.

- Criteria for discontinuation of the study device application

- 1) Acute reactions (allergy, hypersensitivity reactions, etc.) to the study device

- 2) It is determined that continuation of the study is difficult due to an accidental intercurrent condition.
- 3) It is determined that continuation of the study is impossible due to worsening of the pressure ulcer (Stage 4 or higher).
- 4) Debridement was performed during the study, after the study device application.
- 5) Pregnant during the study period
- 6) It is otherwise determined by the investigator that continued application of the study device is not appropriate due to reasons such as serious malnutrition, etc.
- 7) It is determined by the investigator that study participation is not appropriate due to a “serious adverse event”.

“Serious adverse event” is an event, irrespective of a causal relationship with the study device, that is as follows:

- ① Results in death or is life-threatening
- ② Requires inpatient hospitalization or prolongation of existing hospitalization
- ③ Results in persistent or significant disability or dysfunction
- ④ Results in congenital anomaly or birth defect
- ⑤ Other medically important events as identified by the Investigator

In case of discontinuation due to worsening of a pressure ulcer, the treating physician will ensure safety of the patient with appropriate tests and treatment, equivalent to the case of an adverse event.

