## 3. Study Design

---

[figure not shown]
This is a single-center, randomized, 2-arms, open-label pilot study.

Subjects who consent to the study will be assessed for eligibility with screening tests. Subjects can have a 2-week screening period.

After screening, subjects who meet the inclusion/exclusion criteria will apply Medifoam® or Betafoam® for 12 weeks, after randomization. Targeted subjects are outpatient clinic or hospitalized patients. Subjects will make once weekly site visits.

During the treatment period, dressing is performed twice weekly, but additional dressing changes are allowed, depending on the condition of the pressure ulcer, such as excessive exudates at the study ulcer. Nevertheless, the frequency of additional dressing is limited to twice daily. On the weekly site visit days, the investigator(or clinical research coordinator) will change the dressing; on other occasions, the subject or guardian will perform self-dressing. Subjects who achieve complete healing of the target pressure ulcer within 12 weeks will have early completion.

Efficacy assessment is conducted for a total of 12 times at a 1-week interval, after the investigational device application (8d, 15d, 22d, 29d, 36d, 43d, 50d, 57d, 64d, 71d, 78d, 85d). At each efficacy assessment, the investigator (or clinical research coordinator) should take a digital photograph of the target pressure ulcer and retain it as a source document.

---

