## (2) Other endpoints

- ① PUSH reduction rate at each time point

$$\text{Reduction rate} = \frac{\text{PUSH score on 1d} - \text{PUSH score at each time point}}{\text{PUSH score on 1d}} \times 100\%$$

- ② Dressing change frequency during the entire study period

: Calculated as the additional dressing frequency beyond twice daily

- ③ Number of subjects with early completion due to complete healing during the study
- ④ Incidence of new infections at the pressure ulcer until Week 12 based on the CSSC

$$\text{Infection incidence} = \frac{\text{Number of subjects with at least 1 new infection}^{**} \text{ until Week 12, after the study device application}}{\text{Total number of subjects}} \times 100\%$$

(\*\* Infection: Presence of 'Purulent exudates' or 2 or more symptoms of the CSSC. However, for subjects with an infection at baseline, it is defined as development of an additional symptom other than those confirmed at baseline or recurrence of baseline-identified symptoms after being completely healed.)

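### Adverse events and new infections are reported over all subjects with no follow-up time, although subjects leave on healing or discontinuation, so crude comparisons between arms depend partly on who left and when

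*SAP*

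**What the plan says.** **Early exit.** On healing, the Protocol synopsis states: "Subjects who achieve complete healing of the target pressure ulcer within 12 weeks will have early completion". Protocol 14.2 and SAP 5 add that the End-of-Study tests are done at that point and the subject is then finished. For a subject who meets a discontinuation criterion, Protocol 14.1 says "application of the study device and the study should be discontinued". SAP 3 sets the full schedule: "Efficacy assessment is conducted for a total of 12 times at a 1-week interval, after the investigational device application", with visits from 8d to 85d.

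**Detection.** AEs are reviewed at each visit (SAP 7.2), and infection signs are checked at each visit with the CSSC (Protocol 12.2.6). Protocol 17.3 has subjects told to report events. Follow-up under Protocol 17.4 concerns AEs until they resolve or stabilise. Neither document sets a visit or a window for collecting new events after exit.

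**AE measures.** SAP 8 states: "For the number of adverse events and the percentage of subjects who had at least 1 adverse event, present the 95% confidence interval" for each group. Tables 1101 to 1117 show numbers of subjects, percentages and event counts. Table 1101 also has a Fisher p-value between arms. The column labelled incidence rate is a percentage of subjects, and no column carries time.

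**Infection measure.** SAP 7.1 lists "Incidence of new infections at the pressure ulcer until Week 12 based on the CSSC" and divides the number of infected subjects by all subjects. SAP 8 assigns Fisher's exact test to it, although the Table 0707 shell has no p-value column. SAP 9 uses raw data for these endpoints and gives no censoring rule. Kaplan-Meier is planned for healing only.

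**The concern.** Healing is an endpoint of main interest and it also ends observation. If the arms differ in healing or in withdrawals, they also differ in how long subjects were watched for AEs. A count or percentage over all subjects then mixes the weekly risk of an event with the length of observation.

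Two measures are affected:

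- **AEs.** The problem is clearest for the other (non-local) AEs, because healing an ulcer gives no reason for those to stop.
- **Infections.** A subject withdrawn uninfected at Week 3 is counted as uninfected through Week 12, although nobody looked after Week 3.

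The SAP also asks for a confidence interval for the number of AEs. An interval for a count needs a model and an exposure base, and neither is stated.

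Protocol 5.1 says a further trial will build on these results. Crude rates that partly reflect exit patterns could therefore be carried forward.

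**Working it through.** The documents give no AE, infection or exit rate, so there is no planned figure to reproduce. The check asks what the planned measures show when the true weekly risk is the same in both arms.

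**Inputs from the documents.** Protocol Section 9 gives the size: "The target number of subject enrollment is 20 subjects, with 10 subjects per group". It also says "no formal sample size calculation will be conducted". Planned follow-up is 12 weeks.

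**Assumed inputs.** Event rates, the number of leavers and the time of leaving. Rates are constant over time and exit is unrelated to AEs.

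**1. Simple case.** Rate 0.03 per week, 10 subjects per arm.

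- No leavers: 10 × 12 = 120 subject-weeks; 0.03 × 120 = 3.6 expected events; percentage with an event 1 − exp(−0.03 × 12) = 30.2%.
- 5 of 10 leave at Week 6: 5 × 12 + 5 × 6 = 90 subject-weeks; 0.03 × 90 = 2.7 events, 25% fewer. For leavers the percentage is 1 − exp(−0.03 × 6) = 16.5%; the average of 16.5% and 30.2% is 23.4%.
- The gap is 30.2 − 23.4 = 6.8 points, or about 0.7 of one subject in ten.

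**2. Range.** With 3 leavers at Week 8 there are 7 × 12 + 3 × 8 = 108 subject-weeks, 10% below 120. With 5 leavers at Week 4 there are 5 × 12 + 5 × 4 = 80, 33% below. Expected counts fall by the same 10% to 33% whatever the weekly rate, because they are proportional to subject-weeks.

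**3. Leavers in both arms.** Let r be the 12-week risk and f the share leaving at week t. Hazard h = −ln(1 − r)/12. Crude proportion = f × (1 − exp(−h × t)) + (1 − f) × r. Subject-weeks = 10 × (f × t + (1 − f) × 12).

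With r = 40%, h = 0.0426. With t = 6:

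| | 50% leave | 10% leave |
|---|---|---|
| Crude % with an event | 31.3% | 38.3% |
| Subject-weeks | 90 | 114 |
| Expected events | 3.83 | 4.85 |
| Events per 100 subject-weeks | 4.26 | 4.26 |

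The count ratio is 90/114 = 0.79 although the true rate ratio is 1.00. Dividing by subject-weeks removes the gap.

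The same calculation was run for r = 20%, 40% and 60%, leaving shares of 50% vs 10%, 30% vs 10% and 60% vs 20%, and t = 4, 6 and 8. In all 27 combinations the arm with more leavers had the lower crude figures. The gap ran from 1.2 to 13.5 percentage points and the count ratio from 0.69 to 0.93.

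**4. Reversed direction.** Suppose 30% of one arm withdraw because of an AE that is counted, and the other 70% have a 40% risk. That arm shows 0.30 × 1 + 0.70 × 0.40 = 58%, against 40% in an arm with no such withdrawals. It now looks worse.

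**5. Sampling error.** The exact 95% interval for 4 of 10 is 12% to 74%. Fisher's p is 1.00 for 3/10 vs 4/10, and 0.087 for 0/10 vs 4/10.

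**The case against.** Four points on the other side have weight.

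- **Direction.** A reader might infer that the arm with more early leavers will look safer. The documents do not support that as a general statement. Several criteria in Protocol 14.1 are themselves AE-related: acute reactions to the device, serious AEs, and ulcer worsening, which is handled like an AE. Such subjects will usually have been counted with an event before they left. This stands, and step 4 above shows the reversal.
- **Infection after healing.** A reader might take the lower infection percentage in a faster-healing arm as pure artefact. The endpoint is infection at the ulcer, and complete healing means full epithelial cover with intact skin. A healed subject no longer has that open ulcer, so for healed subjects the all-subject proportion is a legitimate cumulative incidence. This stands. It applies in part to local AEs too. It does not cover withdrawn subjects or other AEs.
- **Recoverability.** A reader might conclude that observation time cannot be recovered. It can, roughly. Table 0102 lists discontinuation dates by subject, and Table 0602 summarises days to healing. Tables 0901 and 0902 give N by visit and arm, and adding the N from Visit 3 to Visit 14 approximates subject-weeks apart from missed visits. What is missing is a planned summary and any safety measure that uses it.
- **Size.** This is an exploratory pilot of 20 subjects, and Protocol 16.2 plans no formal test. The artefact is small next to the random error. This stands as to severity. But the SAP does plan between-arm p-values, and the crude figures will be read as a comparison.

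The Week 12 limit is attached to the infection endpoint only; the AE text states no time window.

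**Conclusion.** The point holds in a limited form. By design, observation time varies from about 1 to 12 weeks, and the planned AE and infection measures ignore it. Crude results therefore depend on exit patterns. With equal weekly risk and exit unrelated to AEs, the arm with more early leavers can look safer; with AE-caused exit the bias can go the other way. The artefact is clearest for other AEs and for withdrawn subjects.

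Its size is modest under the assumed inputs and smaller than sampling error at 10 per arm. Withdrawn subjects are not replaced (Protocol Section 9: "Even if a subject is withdrawn from the study, the subject will not be replaced"), so lost observation time is not made up. This affects how the safety tables are read and does not undermine the study. It is worth correcting because the correction is cheap.

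**What to change.** 1. Add to SAP 8 and the SAP 12 table list a by-arm summary of days observed, with one defined end: from 1d to the exit or V14 visit.
2. In Table 1101, keep the planned counts and percentages. Beside them give events per 100 subject-weeks and subjects with a first event per 100 subject-weeks, with an exact Poisson 95% interval for first events only, because repeat events in one subject are not independent. For first events, stop each subject's time at the event or at exit.
3. For Table 0707, add the cumulative incidence of first new infection, with healing as a competing event and censoring at withdrawal for other reasons. Simply censoring at healing would overstate infection risk, because it treats healed subjects as still at risk. Censoring at withdrawal assumes that those who left would have had the same later risk as those who stayed; say so.
4. State beside the planned infection percentage that it assumes no infection after exit.

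**Cost.** One small table, a few added columns and SAP wording, with no change to visits or procedures. It needs first-application and exit dates. The plan already counts time from 1d and lists discontinuation dates; that the remaining visit dates are in the CRF is an assumption, since the CRF is not among the documents. The downside is slightly more programming and rates that will be imprecise at this sample size.

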### **(2) Laboratory test findings**

For continuous data, present descriptive statistics (mean, standard deviation, median, minimum, maximum) by group and time point. In addition, tabulate the proportion of normal/abnormal results by time point in each group.

### **(3) Vital signs**

For continuous variables, present descriptive statistics (mean, standard deviation, median, minimum, maximum) for the baseline and end-of-study test findings by group and visit time point.

---

---

## 9. Handling Missing Values

---

---

For subjects with a missing value during the study or who are withdrawn from the study prior to study completion, efficacy analysis will be conducted by applying the LOCF (Last observation Carried Forward), only in case such subjects have available endpoints of main interest assessment results after the investigational device application. However, in case of missing values for other endpoints and safety endpoints, raw data will be used for analysis, without applying LOCF.

---

---

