15.1 General principles of result analysis

Data obtained from subjects in this study will be analyzed as the SS(Safety Set) and the FAS(Full Analysis set).

- 1) In the SS(Safety set), data obtained from subjects who were enrolled in the study, had at least

- 1 application of the study device, and had at least 1 safety assessment will be analyzed.
- 2) In the FAS(Full analysis set), data obtained from subjects who were enrolled in the study, had at least 1 application of the study device and then had at least 1 available endpoints of main interest review will be included in analysis.

Efficacy and demographics will be analyzed using the FAS and safety data will be analyzed using the SS.

For subjects with a missing value during the study or who are withdrawn from the study prior to study completion, efficacy analysis will be conducted by applying the LOCF (Last Observation Carried Forward), only in case such subjects have available endpoints of main interest assessment results after the investigational device application. However, in case of missing values for Other endpoints and safety endpoints, raw data will be used for analysis, without applying LOCF.

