#### - Criteria for discontinuation of the study device application

- 1) Acute reactions (allergy, hypersensitivity reactions, etc.) to the study device
- 2) It is determined that continuation of the study is difficult due to an accidental intercurrent condition.
- 3) It is determined that continuation of the study is impossible due to worsening of the pressure ulcer (Stage 4 or higher).
- 4) Debridement was performed during the study, after the study device application.
- 5) Pregnant during the study period
- 6) It is otherwise determined by the investigator that continued application of the study device is not appropriate due to reasons such as serious malnutrition, etc.
- 7) It is determined by the investigator that study participation is not appropriate due to a "serious adverse event".

"Serious adverse event" is an event, irrespective of a causal relationship with the study device, that is as follows:

- ① Results in death or is life-threatening
- ② Requires inpatient hospitalization or prolongation of existing hospitalization

- ③ Results in persistent or significant disability or dysfunction
- ④ Results in congenital anomaly or birth defect
- ⑤ Other medically important event as identified by the Investigator

In case of discontinuation due to worsening of a pressure ulcer, the treating physician will ensure safety of the patient with appropriate tests and treatment, equivalent to the case of an adverse event.

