### **7.1 Efficacy Endpoints**

#### **(1) Endpoints of main interest**

- ① Number of patients with complete healing# of ulcer within 12 weeks  
: Subjects who achieved complete healing and had early completion or completion at the end of 12

weeks will be included.

- ② Time to complete healing# of ulcer within 12 weeks

: Time to complete healing is calculated as the number of days from baseline (1d).

(# The definition of complete healing: Epithelial tissue covering 100% of the study ulcer, no abrasion or ulceration, intact dermis and epidermis)

- ③ Pressure ulcer size by each time point
- ④ Pressure ulcer size reduction rate based on a scale at each time point

Reduction Rate=

$$\frac{\text{Pressure ulcer size on 1d}^* - \text{Pressure ulcer size at each time point from 8d to End-of-Study}^{**}}{\text{Pressure ulcer size on 1d}} \times 100\%$$

\* Using a scale-based pressure ulcer area (cm^2) measured prior to the study device application

\*\* Using a scale-based pressure ulcer area (cm^2) without re-epithelization\*\*\* measured at each time point after the study device application

(\*\*\*Re-epithelization: New epithelial tissue covering the pressure ulcer, with no exudate, transudate, or avascular tissue)

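### LOCF carries a fixed ulcer size to Week 12 for subjects withdrawn for worsening or debridement, with no failure rule or sensitivity analysis, and the protocol conflicts on whether an exit size is measured

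*SAP*

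**What the plan says.** - **Missing-data rule.** SAP 9 covers subjects with a missing value and those who leave the study early: "efficacy analysis will be conducted by applying the LOCF (Last observation Carried Forward"). Protocol 15.1 agrees, and both require a finding from after the device was first applied: "efficacy analysis will be conducted by applying the LOCF (Last Observation Carried Forward), only in case such subjects have available endpoints of main interest assessment". Neither separates withdrawals by reason. The rule has one boundary: "in case of missing values for other endpoints and safety endpoints, raw data will be used for analysis, without applying LOCF".
- **Endpoints covered.** SAP 7.1 lists "Pressure ulcer size reduction rate based on a scale at each time point", and ulcer size itself, among the endpoints of main interest, so LOCF applies to both. SAP 8 compares the arms by t-test. Tables 0603 and 0604 report each visit through Visit 14.
- **Withdrawal for failure.** Under SAP 5 and protocol 14.1, criterion 3 is that "continuation of the study is impossible due to worsening of the pressure ulcer (Stage 4 or higher"), and criterion 4 is "Debridement was performed during the study, after the study device application". Meeting either one ends both device use and study participation, so no later weekly sizes are planned.
- **Who stays in.** The FAS (SAP 6) keeps anyone with one application and one later review of an endpoint of main interest. Protocol 9 plans 10 subjects per arm without replacement.
- **Measurement at withdrawal.** The double-asterisk footnote to the protocol's Schedule of study activities gives withdrawn subjects, like healed ones, the full Visit 14 test set, which includes ulcer size. Section 12.1.4 limits an early Visit 14 to subjects whose ulcer has healed. Section 14.1 asks only that the reason and findings be recorded.

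Neither document defines a treatment-failure rule for size, a sensitivity analysis or a count of imputed values.

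**The concern.** Carrying forward 0 cm² for a healed subject is reasonable. A subject withdrawn under criterion 3 or 4 has, on the plan's own terms, gone the wrong way. Yet that subject supplies one fixed area to every later row of Tables 0603 and 0604. If the area was last measured before the ulcer worsened or was debrided, a failure is reported as a partial response through Week 12.

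The stakes come from the small arms and the intended use. One subject is a tenth of an arm mean. The study is open-label, so decisions to debride or withdraw are made with the arm known, and the number of failures could differ between arms. Protocol 5.1 says a further trial will draw on these results.

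**Working it through.** The documents give no withdrawal rate, expected ulcer size or planned effect, so there is no figure of theirs to reproduce. What follows illustrates the rule under assumed values.

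**From the documents:** n = 10 per arm (protocol 9); reduction rate = (size on day 1 − size at visit) / size on day 1 × 100 (SAP 7.1).

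**Assumed:** k = 1, 2 or 3 subjects in an arm withdrawn under criterion 3 or 4; the other subjects average a 60% reduction; carried and Week 12 values as shown.

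**Formula:** error in the arm mean = (k/n) × (carried value − value Week 12 would have shown). The 60% cancels out of the error.

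**(a) A size from before the failure is carried.** Carried +20%, Week 12 would have been −20%:

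| k | LOCF mean | Mean with Week 12 values | Error |
|---|---|---|---|
| 1 | (9×60 + 20)/10 = 56% | (9×60 − 20)/10 = 52% | +4 |
| 2 | (8×60 + 40)/10 = 52% | (8×60 − 40)/10 = 44% | +8 |
| 3 | (7×60 + 60)/10 = 48% | (7×60 − 60)/10 = 36% | +12 |

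Over carried values of 0 to +40% and Week 12 values of 0 to −50%, the error for k = 1 runs from (0 − 0)/10 = 0 to (40 + 50)/10 = 9 points. For k = 3 it runs from 0 to 27 points.

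**(b) A worsened exit size is carried (−20%).** For k = 1, 2, 3:
- Week 12 stays at −20%: error 0.
- Week 12 falls to −50%: +3, +6, +9 points.
- Week 12 recovers to 0%: −2, −4, −6 points.

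**(c) A subject leaves for another reason while healing.** Carried +30%, Week 12 would have been +80%: (k/10) × (30 − 80) = −5, −10, −15 points. Here LOCF understates the reduction.

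**Between arms, under (a) with k = 3 against k = 1.** LOCF puts the arm with more failures 56 − 48 = 8 points lower. The Week 12 values put it 52 − 36 = 16 points lower. LOCF halves the gap but does not reverse it.

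**Endpoints outside the problem.** For complete healing, a carried status of not healed counts the subject as a non-healer. For PUSH, SAP 9 uses raw data.

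**The case against.** The strongest objection is that the schedule footnote is the only text that says outright what is measured when a subject is withdrawn, and it requires the ulcer assessment. The limit in Section 12.1.4 can be read as merely explaining early completion, which Section 14.2 reserves for healed subjects, and so as silent on withdrawals. On that reading the carried value is the size at failure, and case (b) gives an error of either sign or none. This stands as far as it goes: a reader might infer that LOCF always carries a size from before the failure, and the documents do not establish that. But the two statements conflict on their face, an exit visit can be missed, and SAP 9 does not say which measurement is carried.

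Other parts of the objection also hold:

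- Progression to Stage 4 is defined by exposed bone, tendon or muscle, while size is width times length. An ulcer can deepen without growing in area. A fully observed Week 12 area would miss that too, so this is partly a limit of the area endpoint.
- Scoring failures as 0% is also a single imputation treated as observed, so it understates the standard deviation just as LOCF does. It is not clearly a better replacement.
- LOCF is prespecified in the protocol, the study is exploratory, and Table 0102 lists each discontinued subject with date and reason. A careful reader could trace the cases, though not their effect on the means.

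**Conclusion.** The point holds in a limited form. The rule as written can credit a treatment failure with partial benefit in the size analyses, and nothing planned would show whether it did. For one such subject in an arm of 10, the overstatement is 0 to 9 percentage points. That assumes a carried value of 0 to +40%, taken before the failure, and a Week 12 value of 0 to −50%. With an exit measurement the error may be zero or negative, and withdrawals during healing pull the other way.

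Two stronger readings are not supported. A reader might infer that the arm with more failures is favoured; the working shows it penalised too little, not preferred. A reader might also compare LOCF with a score of no benefit, for example 1×20/10 = 2 to 3×50/10 = 15 points for one to three failures with carried reductions of 20 to 50%. That is the distance between two imputation rules under assumed inputs, not a bias.

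**What to change.** 1. Reconcile the schedule footnote with protocol 12.1.4 on whether the ulcer is assessed at withdrawal. State in SAP 9 that LOCF carries the exit measurement where one is taken, and what it carries where none is. Record whether that measurement came before or after any debridement.
2. Keep the protocol's LOCF analysis of size and reduction rate, and present beside it in Tables 0603 and 0604:
   - (a) an analysis that counts criterion 3 and 4 withdrawals as failures at later visits, either with a reduction of 0% (or the last value if worse) or with the worst rank in a Wilcoxon rank sum test, which the SAP already names;
   - (b) observed cases, with the number of imputed values per visit and arm.
3. State that healed subjects stay at 0 cm² in both added analyses. Otherwise the observed-case rows would lose the best outcomes as subjects complete early.

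The cost is some SAP wording, a protocol clarification and one extra table. The reported reduction may be slightly less favourable.
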